The information gained from this research can directly benefit CKD-5D patients. Reversal of bone loss may result in reduction of bone pain and fracture risk. Moreover, participation in the study and recognition of bone loss may motivate them to adjust their diet and lifestyle and to be more compliant with their therapeutic regimen. The risks of the proposed treatments are well controlled by the careful monitoring protocol. The information gathered from this study will have a direct impact on the clinical management of patients

with CKD-5D at risk for bone loss. The risks from BMD measurements, CAVC measurements and blood draws are small; therefore, the benefits far outweigh the risks.

Based on the knowledge to be gained in the study, we will be able to provide practicing nephrologists with a bone turnover specific individualized treatment regimen for CKD patients with low bone mass. If our treatment regimens prove successful, we will reverse bone loss in these patients thereby reducing fracture risk. There may also be an as yet undetermined retardation of CAVC progression and the associated risk for cardiovascular events in these patients. We will also be able to compare QCT to DXA for measurement of bone mass in these patients and to determine whether DXA, with its lower radiation dose, lower cost and wider availability, can be used in lieu of QCT.

Available Alternative Treatment(s): Describe alternative treatments and procedures that might be advantageous to the subjects, should they choose not to participate in the study. This should include a discussion of the current standard of care treatment(s).

There are currently 3 medications approved for the treatment of osteoporosis; 2 of which are being used in this study. The third medication for osteoporosis is not being used in this patient population of dialysis patients because there have been reports of severe hypocalcemia requiring hospitalization. If the subject chooses not to participate in the study they should continue current standard of care treatment with their primary physician and nephrologist.

[Back to Top](#)

Research Materials, Records and Privacy: Identify the sources of research material obtained from individually identifiable living human subjects. Indicate what information (specimens, records, data, genetic information, etc.) will be recorded and whether use will be made of existing specimens, records or data. Explain why this information is needed to conduct the study.

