Adverse events (AE's). Adverse events are any untoward medical occurrences associated with the use of study drugs, whether or not considered drug related; this includes adverse reactions (AR's) which are undesirable effects reasonably associated with use of a study drug. The severity of all anticipated (see potential risks listed above) and unanticipated AE's and AR's will be graded according to the National Cancer Institute's Common Toxicity Criteria, version 2.0 (CTC-2) (<http://ctep.cancer.gov/reporting/ctc.html>). Study coordinators (certified physician assistants) will record all adverse events at each encounter with the patient and assign a preliminary severity and attribution grade. The PI will review all adverse events and confirm their grading.

The grades of AE and AR severity will be:

0 = No AE/ARs or within normal limits,

1 = Mild AE/AR

2 = Moderate AE/AR

3 = Severe and undesirable AE/AR

4 = Life-threatening or disabling AE/AR

5 = Death related to AE/AR.

The attribution of the AEs and ARs to the study treatments will be graded as:

1 = Unrelated, AE/AR clearly not related to the investigation

2 = Unlikely, AE/AR doubtfully related to the investigation

3 = Possible, AE/AR may be related to the investigation

4 = Probable, AE/AR likely related to the investigation

5 = Definite, AE/AR clearly related to the investigation.

All AEs and ARs will be recorded in the REDCap® database. The investigator and the study coordinators will review the occurrence of mild to moderate AEs and ARs every 3 months. This file will be accessible upon request to the Data and Safety Monitoring Board. All severe or higher (grade 3-5) AEs and ARs (SAEs and SARs) will be reported to the IRB, the Data and Safety Monitoring Board, and the NIH within 48 hours, according to UK policies, and to the FDA in accordance with IND regulations. All unanticipated AEs and ARs, regardless of attribution, will be reported to the IRB, CCTS, DSMB and the NIH in an expedited manner (48 hours) if they are grade 2 or higher in severity.

[Back to Top](#)

Subject Complaints: Describe procedures (other than information provided in consent document) for handling subject complaints or requests for information about the research. The procedures should offer a safe, confidential, and reliable channel for current, prospective, or past research subjects (or their designated representative) permitting them to discuss problems, concerns and questions, or obtain information.

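### Serious adverse events are defined by severity grade alone, so a hospital admission does not by itself trigger an expedited report to the IRB, DSMB or NIH

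*Combined protocol and SAP*

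**What the plan says.** All of this is in the combined protocol and SAP, Data and Safety Monitoring, Safety monitoring, in the paragraphs on adverse events.

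- **Grading.** Severity is graded 0 to 5 by the Common Toxicity Criteria, version 2.0. Grade 1 is mild, 2 moderate, 3 severe, 4 life-threatening or disabling, and 5 death related to the event. Coordinators assign a preliminary grade. The principal investigator reviews all adverse events and confirms the grading.
- **Main expedited rule.** "All severe or higher (grade 3-5) AEs and ARs (SAEs and SARs) will be reported to the IRB". The other recipients on the 48-hour clock are the DSMB and the NIH, under university policies; the FDA is told as the IND regulations require.
- **Second expedited rule.** Unanticipated events, whatever their attribution, go to the IRB, CCTS, DSMB and NIH "in an expedited manner (48 hours) if they are grade 2 or higher in severity". Anticipated events are those among the potential risks listed earlier in the protocol.
- **Everything else.** "The investigator and the study coordinators will review the occurrence of mild to moderate AEs and ARs every 3 months". On the resulting file: "This file will be accessible upon request to the Data and Safety Monitoring Board".

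The preceding part of the same section (plan for monitoring progress) has the DSMB monitor adverse events according to these rules. It also has the investigators and coordinators meet weekly, with coordinators reporting on all patient contacts.

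**The concern.** Severity describes how intense an event is. Seriousness describes what it led to: death, threat to life, admission or a longer stay, disability, or another medically important outcome. The protocol attaches the labels SAE and SAR to a severity band, and no section supplies an outcome-based definition. An admission therefore reaches independent reviewers within 48 hours only if its grade, or its absence from the list of known risks, takes it there.

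Two features make this matter. First, the extra protection at grade 2 is limited to unanticipated events, while the anticipated ones are the known effects of the study drugs. The Potential Risks section lists hypocalcemia with cinacalcet; dizziness and nausea with teriparatide; and reduced calcium, esophageal ulcer, gastritis, vomiting and musculoskeletal pain with alendronate. Moderate events plausibly caused by treatment are thus the ones left without an expedited route. Second, the grade is set within the trial team. Controls receive no study treatment (Research Procedures), so no placebo hides the allocation, and the investigator holds the IND (Study Drug Information). One grading judgment by that team can decide whether an admission goes out within 48 hours.

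**Working it through.** The protocol gives no event rates, so there is nothing to compute. The check is to trace each kind of event through the stated rules and ask whether admission changes its route.

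| Grade | Anticipated (listed risk) | Unanticipated |
|---|---|---|
| 3 to 5 | 48 h to IRB, DSMB, NIH | 48 h to IRB, DSMB, NIH |
| 2 | no expedited report | 48 h to IRB, CCTS, DSMB, NIH |
| 1 | no expedited report | no expedited report |

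Three of the six cells have a 48-hour route and three do not. Admission is not an input to any cell.

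1. **Which outcomes are already covered?** Grade 4 covers life-threatening or disabling events, and grade 5 covers death related to the event. Both fall under the 48-hour rule. Of the usual seriousness criteria, admission or prolonged stay and important medical events are the ones with no counterpart in the grading scale as printed.

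2. **Do the references to outside rules widen the set?** The phrase "within 48 hours, according to UK policies, and to the FDA in accordance with IND regulations" belongs to a sentence whose subject is grade 3 to 5 events. As written, it describes how those events are reported and does not bring in others. The FDA route is left out of this point, because the IND regulations it invokes are not in the documents.

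3. **Does the DSMB's general remit close the gap?** The DSMB monitors adverse events under these same rules. For grades 1 and 2 they give it access to a file on request. No routine transmission to the DSMB is stated.

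4. **What does the trial team itself do?** Events are entered in REDCap, the principal investigator reviews every event with no stated deadline, and mild-to-moderate events are reviewed together every 3 months. Coordinators' reports on patient contacts appear in the paragraph that sets the weekly meetings.

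A coordinator who followed the text exactly would send no expedited report for a patient admitted with an anticipated event graded 2.

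**The case against.** The strongest reply is that the gap is narrow and may seldom be used. Much of this stands. Life-threatening, disabling and event-related fatal outcomes are already expedited, as is any unlisted event from grade 2 upward. What remains is a listed effect graded 1 or 2 that still leads to admission, plus unlisted grade 1 events. Many admissions may be graded 3 or higher. The toxicity criteria and the university policies are not in the documents, so this cannot be checked either way. The reply bears on frequency. It does not supply the missing trigger.

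Three stronger readings are tempting, and the documents do not support them.

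- **A reader might infer that such an event waits up to 3 months for investigator review.** The 3-month step is a grouped review of how often mild and moderate events occur. The principal investigator separately reviews every event, and the team meets weekly. Setting 3 months against 48 hours would compare an internal review cycle with an external reporting deadline.
- **A reader might infer that these events are never reported.** What is missing is an expedited report. The DSMB can ask for the file, and an adverse event log dated October 2019 is listed among the IRB application files, though its content is not shown.
- **A reader might point to Available Alternative Treatment(s)**, which sets aside a third drug because "there have been reports of severe hypocalcemia requiring hospitalization". Severe is grade 3 on the protocol's scale, so an event of that description would already be expedited. It is not an example of the gap.

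**Conclusion.** The point holds in a limited form. Seriousness is tied to severity grade, and neither admission, prolonged stay nor medical importance is a reporting trigger. An admission graded 1 or 2 for an anticipated risk, or graded 1 if unanticipated, has no 48-hour route to the IRB, DSMB or NIH. The DSMB reaches it only on request, and the principal investigator's review of the individual event has no stated deadline.

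The size is structural: three of six rule combinations lack an expedited route. The number of patients affected cannot be determined, because the documents give neither admission rates nor the grading criteria, and no percentage should be attached.

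The conclusion assumes that the written rules are what staff follow, and that the university policies cited, which are not in the documents, do not separately require expedited reports of admissions. It is a should-fix point: it concerns the timing and routing of safety reports, and bears on neither the endpoints nor the analysis.

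**What to change.** In the adverse events paragraphs:

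1. Stop using SAE and SAR as the label for grade 3 to 5 events.
2. Define a serious event by outcome: death, life-threatening, hospital admission or prolongation, disability, or important medical event.
3. Report every serious event to the IRB, DSMB and NIH within 48 hours, whatever its grade and whether or not it was anticipated.
4. Keep the two existing 48-hour rules (grade 3 to 5, and unanticipated grade 2 or higher) alongside.

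For events that meet the definition, the 48-hour limit would also bound the time available for the principal investigator's review.

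The cost is protocol wording, one yes/no field (serious by outcome) on the adverse event form, and more expedited reports, in a number the documents do not allow one to estimate. Treatment, visits and endpoints are unchanged.

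Sending the DSMB the grade 1 and 2 events by randomized group at its regular reviews, instead of on request, would be a useful addition. That is a preference, and the correction does not depend on it.

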If **YES**, you must describe the plan for the management of reporting unanticipated problems, noncompliance, and submission of protocol modifications and interim results from the non-UK sites in the E-IRB "Research Description" section under *Resources*.

If the non-UK sites or non-UK personnel are *engaged* in the research, there are additional federal and university requirements which need to be completed for their participation, such as the establishment of a cooperative IRB review agreement with the non-UK site. Questions about the participation of non-UK sites/personnel should be discussed with the ORI staff at [contact].

RESEARCH ATTRIBUTES

Indicate the items below that apply to your research. Depending on the items applicable to your research, you may be required to complete additional forms or meet additional requirements. Contact the ORI [contact]) if you have questions about additional requirements.

Not applicable

Check All That Apply

- Academic Degree/Required Research
- Aging Research
- Alcohol Abuse Research
- Cancer Research
- Certificate of Confidentiality
- CCTS-Center for Clinical & Translational Science
- Clinical Research
- Clinical Trial
- Clinical Trial Multicenter(excluding NIH Cooperative Groups)
- Clinical Trial NIH cooperative groups (i.e., SWOG, RTOG)
- Clinical Trial Placebo Controlled Trial
- Clinical Trial UK Only
- Collection of Biological Specimens
- Collection of Biological Specimens for Banking
- Community-Based Participatory Research
- Data & Safety Monitoring Board
- Data & Safety Monitoring Plan
- Deception
- Drug/Substance Abuse Research
- Educational/Student Records (e.g., GPA, test scores)
- Emergency Use (Single Patient)
- Genetic Research
- Gene Transfer
- GWAS (Genome-Wide Association Study) or NIH-funded study generating large scale genomic data
- International Research
- Internet Research
- Planned Emergency Research Involving Waiver of Informed Consent
- Pluripotent Stem Cell Research
- Recombinant DNA
- Survey Research
- Transplants
- Use of radioactive material, ionizing radiation, or x-rays [Radiation Safety Committee review required]
- Vaccine Trials

Click applicable listing(s) for additional requirements and/or information:

- [Cancer Research \(MCC PRMC\)](#)
- [Certificate of Confidentiality](#) (look up "Confidentiality/Privacy...")
- [CCTS \(Center for Clinical and Translational Science\)](#)
- [Clinical Research](#) (look up "What is the definition of....")
- [Clinical Trial](#) (look up "What is the definition of....")

Determine if research meets [NIH definition of clinical trial](#);

*Reminder: Ensure compliance with [clinicaltrials.gov](#) registration requirements for applicable clinical trials and [Good Clinical Practice \(GCP\) training](#) requirements.

- [Collection of Biological Specimens for Banking](#) (look up "Specimen/Tissue Collection...")
- [Collection of Biological Specimens](#) (look up "Specimen/Tissue Collection...")
- [Community-Based Participatory Research](#) (look up "Community-Engaged...")
- [Data & Safety Monitoring Board](#) (DSMB)

*For Medical IRB: [Service Request Form](#) for CCTS DSMB

- [Data & Safety Monitoring Plan](#)
- [Deception*](#)

*For deception research, also go to the E-IRB Application Informed Consent section, checkmark and complete "Request for Waiver of Informed Consent Process"

- [Emergency Use \(Single Patient\) \[attach Emergency Use Checklist\]](#) (PDF)
- [Genetic Research](#) (look up "Specimen/Tissue Collection...")
- [Gene Transfer](#)
- [HIV/AIDS Research](#) (look up "Reportable Diseases/Conditions")
- [Screening for Reportable Diseases \[E2.0000\]](#) (PDF)
- [International Research](#) (look up "International & Non-English Speaking")
- [NIH Genomic Data Sharing \(GDS\) Policy](#) (PDF)
- [Planned Emergency Research Involving Waiver of Informed Consent*](#)

*For Planned Emergency Research Involving Waiver of Informed Consent, also go to the E-IRB Application Informed Consent section, checkmark and complete "Request for Waiver of Informed Consent Process"

- [Use of radioactive material, ionizing radiation or](#)

FUNDING/SUPPORT

If the research is being submitted to, supported by, or conducted in cooperation with an external or internal agency or funding program, indicate below all the categories that apply. [?](#)

Not applicable

Check All That Apply

- Grant application pending
- (HHS) Dept. of Health & Human Services
 - (NIH) National Institutes of Health
 - (CDC) Centers for Disease Control & Prevention
 - (HRSA) Health Resources and Services Administration
 - (SAMHSA) Substance Abuse and Mental Health Services Administration
- (DoJ) Department of Justice or Bureau of Prisons
- (DoE) Department of Energy
- (EPA) Environmental Protection Agency
- Federal Agencies Other Than Those Listed Here
- Industry (Other than Pharmaceutical Companies)
- Internal Grant Program w/ proposal
- Internal Grant Program w/o proposal
- National Science Foundation
- Other Institutions of Higher Education
- Pharmaceutical Company
- Private Foundation/Association
- U.S. Department of Education
- State

Other:

Click applicable listing(s) for additional requirements and/or information:

- [\(HHS\) Dept. of Health & Human Services](#)
- [\(NIH\) National Institutes of Health](#)
- [\(CDC\) Centers for Disease Control & Prevention](#)
- [\(HRSA\) Health Resources & Services Administration](#)
- [\(SAMHSA\) Substance Abuse & Mental Health Services Administration](#)
- Industry (Other than Pharmaceutical Companies) [[IRB Fee Info](#)]
- [National Science Foundation](#)
- [\(DoEd\) U.S. Department of Education](#)
- [\(DoJ\) Department of Justice or Bureau of Prisons](#)
- [\(DoE\) Department of Energy Summary and Department of Energy Identifiable Information Compliance Checklist](#)
- [\(EPA\) Environmental Protection Agency](#)

Specify the funding source and/or cooperating organization(s) (e.g., National Cancer Institute, Ford Foundation, Eli Lilly & Company, South Western Oncology Group, Bureau of Prisons, etc.):

Add Related Grants

If applicable, please search for and select the OSPA Account number or Electronic Internal Approval Form (eIAF) # (notif #) associated with this IRB application using the "Add Related Grants" button.
If required by your funding agency, upload your grant using the "Grant/Contract Attachments" button.

[Add Related Grants](#)

[Grant/Contract Attachments](#)

The research involves use of Department of Defense (DoD) funding, military personnel, DoD facilities, or other DoD resources.

(See DoD SOP [[PDF](#)] and DoD Summary [[PDF](#)] for details)

Yes No

Using the “attachments” button (below), attach applicable materials addressing the specific processes described in the DoD SOP.

[DOD SOP Attachments](#)

Additional Certification: (If your project is federally funded, your funding agency may request an Assurance/ Certification/Declaration of Exemption form.) Check the following if needed:

Protection of Human Subjects Assurance/Certification/Declaration of Exemption (Formerly Optional Form – 310)

OTHER REVIEW COMMITTEES

If you check any of the below committees, additional materials may be required with your application submission.

Does your research fall under the purview of any of the other review committees listed below? [If yes, check all that apply and attach applicable materials using the attachment button at the bottom of your screen.]

Yes No

Additional Information	
 Institutional Biosafety Committee  Radiation Safety Committee  Radioactive Drug Research Committee  Markey Cancer Center (MCC) Protocol Review and Monitoring Committee (PRMC)  Graduate Medical Education Committee (GME)  Office of Medical Education (OME)	
 • Institutional Biosafety Committee (IBC)--Attach required IBC materials • Radiation Safety Committee (RSC)-- For applicability, see instructions and/or upload form [WORD] [PDF] • Radioactive Drug Research Committee (RDRC)--information • Markey Cancer Center (MCC) Protocol Review and Monitoring Committee (PRMC)**--Attach MCC PRMC materials, if any, per instructions • See requirement of Office of Medical Education (OME) • See requirement of Graduate Medical Education Committee (GME)
Attachments	

** If you are proposing a study involving cancer research, be sure to have "Cancer Research" marked in the E-IRB "Research Attributes" section. If your study involves cancer research, ORI will provide a copy of your research protocol to the Markey Cancer Center (MCC) Protocol Review and Monitoring Committee (PRMC). The MCC PRMC is responsible for determining whether the study meets the National Cancer Institute (NCI) definition of a clinical trial and for issuing documentation to you (the investigator) which confirms either that PRMC approval has been obtained or that PRC review is not required. Your IRB application will be processed and reviewed independently from the PRMC review.
	

ADDITIONAL INFORMATION/MATERIALS

Do you want specific information inserted into your approval letter? Yes No

Approval Letter Details (e.g., serial #):

Submission Description: If you wish to have specific details included in your approval letter (e.g., serial #, internal tracking identifier, etc...), type in the box below exactly what you wish to see on the approval letter. What you type will automatically appear at the top of all approval letters, identical to how you typed it, until it is changed by you (Hint: don't include instructions or questions to ORI staff as those will appear in your approval letter). **If these details need to be changed as a result of revisions, continuation review, or modifications to the application, you are responsible for updating the content of the field below accordingly.**

Please verify that the information in the Approval Letter Details (e.g., serial #) subsection of the Additional Information/Materials section is correct for this modification request.

Informed Consent Comment by [name] - PI to PI on 2/12/2020 12:09:11 PM

Please see the IRB stamp has been removed and the tracked changes also has been uploaded.

Informed Consent Comment by [name] - ORI to PI on 2/12/2020 11:23:41 AM

Please provide a tracked changes version of the Treatment consent showing changes made to the previously approved version to the current proposed version.

Informed Consent Comment by [name] - ORI to PI on 2/12/2020 11:22:08 AM

Please remove the IRB stamp in the upper right hand corner of pages 2 through 13 from the CLEAN version of the Treatment Consent provided
